We will perform the following measurements in our effort to explain differences in protein synthesis in muscle and understand regulation of the MHC genes in humans with obesity versus the lean controls: plasma and muscle insulin growth factor 1 (IGF-1) and associated hormones (i.e., growth hormone) and binding proteins that determine the IGF-1 function; plasma cytokines, such as TNF α , IL-6, IL-8, IL-10 (cytokine measurements will be performed by [name] laboratory at ASU); chromatin-associated modification in isolated DNA from the muscle samples (DNA modification measurements will be performed by [name] laboratory at Mayo Clinic-Arizona). We will identify mechanisms involved in the responses we observe in vivo (i.e., differences in protein synthesis and MHC isoform expression between muscle from lean subjects and muscle from subjects with obesity) by performing in vitro, cell culture experiments, and where myoblasts isolated from the muscle biopsy samples are propagated to myotubes and associated changes in protein synthesis and MHC in response to changes in the expression of regulatory factors (i.e., IGF-1) can be modified in the absence of any other hormonal or metabolic differences.

Real-time quantitative PCR determination of gene expression. Expression of genes in skeletal muscle will be determined following procedures we have previously described (7, 8). Briefly, isolated mRNA will be purified using the RNeasy MinElute Cleanup Kit and be used to perform cDNA synthesis using the ABI High Capacity cDNA Reverse Transcription kit. Real time PCR will be performed on an Applied Biosystems 7900HT Fast Real-Time PCR System using pre-designed TaqMan® gene expression assays (probe/primer sets from ThermoFisher Scientific), and by following the manufacturer's protocols. The mRNA levels will be normalized to GAPDH, and relative differences in the mRNA levels will be analyzed by the $2^{-\Delta\Delta CT}$ method. miRNA-208b and miRNA-499 in muscle will be quantified following procedures we have previously described (7), and normalized to RNU-6B. Blood chemistry parameters will be quantified using commercially available assays and kits.

Statistical Design and Power

Our main end-points in the proposed studies are the synthesis rates of mixed-muscle protein, mixed-mitochondrial protein, as well as MHC isoforms, particularly MHC-I, whose synthesis rate we found to be lower in subjects with obesity, in our preliminary studies. These preliminary data also show that MHC-I synthesis rate does not increase in response to our experimental manipulation (i.e., exercise stimulus alone) despite an increase in MHC-I mRNA. Therefore, other main end-points are the expression of mRNA of MHC isoforms as well as the formation of the active eIF4F complex, which has key role in translation initiation in skeletal muscle, and which we found in our preliminary studies to be lower in muscle from humans with obesity. Statistical significance will be calculated using 2-way repeated measures ANOVA.

We will study equal number of males and females. We have detected a difference of 1.1 SD with respect to eIF4F complex formation in the Basal state between subjects with obesity and lean controls. Therefore, a sample of 17 subjects with obesity and 17 lean subjects will have sufficient power (80%) to detect 1.1 SD difference ($\alpha = 0.05$) in eIF4F complex formation, and also will have >95% power ($\alpha = 0.05$) to detect a difference of 2.0 SD and 3.5 SD with respect to the rates of mixed-muscle protein synthesis and breakdown, respectively. Also, in the Basal state, we have detected a difference of 2.9 SD for MHC-I synthesis between groups, suggesting that 17 subjects/group will have >95% power to detect this difference ($\alpha = 0.05$). With respect to mRNA responses in the Basal state, we have detected a difference of 1.26 SD for MHC-IIx expression suggesting that a sample of 17 subjects/group will have >80% power to detect significant difference in this variable between groups ($\alpha = 0.05$). We have reported a difference of 2.3 SD in increasing mixed-muscle protein synthesis with increased plasma amino acid concentrations alone in humans with obesity (8). Considering a conservative estimate of a difference of at least half of that (i.e., 1.15 SD) in the response of the MHC-I, 17 subjects/group will provide >90% power ($\alpha = 0.05$) to detect statistically significant increase from Basal in the rate of synthesis of MHC-I in response to the increase in plasma amino acid concentrations coupled to the exercise stimulus in the subjects with obesity ($\alpha = 0.05$). We will test another 17 subjects with obesity that will serve as controls (i.e., increase in plasma amino acid concentrations alone), for a total of 34 subjects with obesity participating in the study. The same experiments will be performed in lean subjects, and where 17 subjects will undergo increase in plasma amino acid

Date: February 23, 2024

Protocol V11

concentrations coupled to the exercise stimulus, and another 17 will serve as controls, for a total 34 lean subjects participating in the study. Main outcome in the exercise-alone studies is the increase in MHC-I mRNA expression after aerobic exercise, and which we show to increase only in the subjects with obesity. In our preliminary studies we detected a difference of 0.94 SD for MHC-I mRNA expression between before and after exercise in subjects with obesity. A sample of 9 subjects per group will have sufficient power (80%) to detect 0.94 SD difference ($\alpha = 0.05$) in MHC-I mRNA expression. Therefore, we will study 9 lean subjects and 9 subjects with obesity in the groups that will undergo exercise-alone trial. Sample size estimates and power were calculated using paired t-tests with an overall $\alpha = 0.05$ and $\alpha = 0.0125$ for Bonferroni-adjusted multiple comparisons. We propose to enroll 2 more subjects/group for the amino acid infusion and exercise+amino acid infusion studies (to the overall 34 subjects per group indicated above for those studies), to account for unsuccessful experiments and/or increase the statistical power in pair-wise comparisons with the lowest effect size, for a total of 36 lean subjects and 36 subjects with obesity for the studies related to the amino acid infusion and exercise+amino acid infusion. Therefore, we will enroll a total of 90 subjects.

Protection of Human Subjects

Risks to Human Subjects

Human Subjects Involvement, Characteristics, and Design

We will study 90 subjects (18-45 years old at the time of enrollment). All subjects will be studied in association with a day-long infusion study, and while resting in bed. All subjects, and as part of their participation in the study, will undergo physical/cycle ergometry exercise for 45 mins, and which will be performed approximately halfway during the infusion study. Subjects recruited for these studies will be representative of the ethnic and racial makeup of the Greater Phoenix Metropolitan Area in Arizona. Because of the invasive nature of the studies, and because muscle protein metabolism can differ during growth in children that may confound our findings, children will not be included in this project. Subjects will first be screened over the phone, and if they meet the initial criteria, they will be invited to sign a consent form. They will be invited for complete screening at the Clinical Studies Infusion Unit (CSIU) at Mayo Clinic in Arizona. Screening at the CSIU will include the following: (i) physical examination and medical history; (ii) electrocardiogram (ECG); (iii) blood tests including complete cell count and liver function, blood glucose, triglycerides, cholesterol and electrolytes; (iv) urinalysis; (v) urine pregnancy test (women); and (vi) 2-hour oral glucose tolerance test (OGTT). If the subject qualifies, they will be invited on a separate date to first undergo determination of body composition, followed by a cycle ergometer test to exhaustion to determine peak oxygen uptake (VO_{2peak}). Diet and physical activity will be evaluated as part of these screening procedures. The inclusion/exclusion criteria for subject participation include:

Inclusion Criteria:

- age, 18-45 years old
- ability to sign informed consent form
- body mass index (BMI), 18.0 – 26.0 kg/m² (lean subjects), 32.0-50.0 kg/m² (subjects with obesity)

Exclusion Criteria:

- evidence of diabetes
- presence of acute illness
- history of liver disease
- uncontrolled metabolic disease, including renal disease
- heart disease related to atrial fibrillation, history of syncope, limiting or unstable angina, congestive heart failure or ECG documented abnormalities such as >0.2 mV horizontal or downsloping ST-segment depression, or frequent arrhythmias (>10 premature ventricular contractions/min)
- low hemoglobin or hematocrit
- use of anabolic steroids or corticosteroids (within 3 months)
- not classified as inactive/sedentary based on accelerometry/ActivPal data (i.e., physical activity > 1.7 METs).
- current participation in a weight-loss regimen
- extreme dietary practices (i.e., vegan, vegetarian)
- smoking (including electronic cigarettes and marijuana) subjects will be included as long as they are willing to abstain for 5 days prior to screening and infusion studies.
- pregnancy - women trying to become pregnant will be excluded from the study; women of child-bearing-potential will be able to participate in this study only if they have a negative pregnancy test and agree to use acceptable birth control during the course of the study [surgical sterilization, approved hormonal contraceptives (such as birth control pills, Depo-Provera), barrier methods (such as a condom or diaphragm) used with a spermicide, an intrauterine device (IUD), abstinence].
- gastro-intestinal surgery
- any medication, intake of supplements, other condition, or event considered exclusionary by the PI and the study physician.

Sources of Materials

Research material obtained from subjects will consist of blood, muscle and urine samples and the data resulting from the analysis of said samples. In addition, research material includes data resulting from the

Date: February 23, 2024

Protocol V11

measurements of body composition using Dual-energy X-ray Absorptiometry (DEXA), as well as the measurements of expired gases during exercise. All research material will be used explicitly for the purpose of this research. All data will be stored electronically and/or in hardcopy format and will be available only to members of the research team for the purposes of the research being conducted.

Potential Risks

Potential risks from participation in the study include problems associated with peripheral catheter insertion, infusions of stable isotopes and medications, blood drawing, muscle biopsy, abnormal blood pressure response during exercise. Subjects will be withdrawn from the study if any of the side effects are displeasing to them and they do not wish to continue the study, or they meet any of the previously described subject exclusion criteria (above), or the study physician determines that there is a reason to discontinue participation.

Adequacy of Protection Against Risks Recruitment and Informed Consent

Research will be initiated only after obtaining approval from the Institutional Review Board (IRB) at Mayo Clinic. We plan on using a variety of recruitment procedures that include advertisement through flyers and online postings on the Arizona State University and the two Mayo Clinic campuses in Arizona, as well as through our subject registry within the Metabolic Program at Mayo Clinic in Arizona. Recruitment of subjects will also be done using physician referrals of participants in our Weight and Wellness Solution program at Mayo Clinic in Arizona.

A member of the study team will explain all experiment-related procedures and risks thoroughly to each subject. Before informed consent is obtained, subjects will be encouraged to thoroughly read the informed consent form and ask questions regarding the outlined procedures and risks. If a subject agrees to participate as a study volunteer and to sign the informed consent form, signature will be obtained in the presence of the principal investigator/co-investigators, postdoctoral fellow, study coordinator, or a CSIU nurse for witness purposes. The signed consent form will be kept on file in the CSIU or the Metabolic Program within the Mayo Clinic Research unit and a copy will be given to the subject.

Protections Against Risk

General Screening: All subjects will have an assessment of their medical history and will undergo a comprehensive physical exam at the time of enrollment. Subjects will be screened with a routine physical examination, blood tests including cell count and liver function, urinalysis, blood glucose, electrolytes, and electrocardiogram. [name], will examine the screening results and initial to denote approval for enrolling the subject in the study. Records of approval for enrollment will be kept on file in the CSIU or the Metabolic Program.

Study Procedures: All procedures will be performed by appropriately trained and credentialed personnel under the supervision of [name].

Blood Sampling: Blood samples will be collected solely for the purpose of experimentation. The blood will be used to measure the concentration of various plasma substances such as amino acids, insulin, glucose, as well as leucine and phenylalanine stable isotope enrichments. The amount of blood taken during each infusion study will be no more than approximately 150 mL (~300 mL for both visits), which is well below the amount (~ 500 mL) taken during a typical blood donation. Saline will be given as replacement during the data collection protocol and subjects will have no noticeable effects.

Muscle Biopsies: Muscle samples will be collected using strict sterile procedures from the lateral portion of the vastus lateralis muscle. This tissue will be used to measure enrichment of muscle free amino acids and muscle proteins with stable isotopes. Prior to taking the muscle biopsy, the skin will be numbed with EMLA cream (2.5% lidocaine and prilocaine 2.5%) for approximately 15 min. The skin will then be cleaned with topical antiseptic (i.e., Betadine, Chloraprep) and the skin and tissue below injected with local anesthetic (lidocaine) to eliminate any pain. A small incision will be made through the skin through which a 6mm Bergström needle will be advanced into the muscle and suction applied. A piece of muscle (~150 mg/per biopsy) will then be removed with the needle, and the skin will be closed with Steristrips. To minimize the risk of infection and bruising, an antibiotic

Date: February 23, 2024

Protocol V11

ointment and pressure dressing will be applied, respectively. The risks of this procedure involve pain, which will be minimized by the injection of local anesthetic, and the possible formation of a bruise from localized bleeding. As with any medication, allergic reactions are possible; allergic reactions to the numbing medicine could cause problems such as a skin sore, swelling, or hives. Bleeding from the biopsy site is highly unlikely since no major artery or vein is located in the area of the vastus lateralis. The most likely complication of this procedure is infection due to lack of sterility during the procedure. We will minimize the risk of infection by using strict sterile procedures. There is risk of hematoma associated with the muscle biopsy. Bleeding can also be seen as bruising at the place on the leg where the muscle was taken. The swelling or bruising usually goes away with rest within 2-3 days, although sometimes it may take a week. Very rarely some subjects may experience numbness or tingling at the biopsy site. This is usually temporary and goes away in few days. Evidence for hematoma at the muscle biopsy site will be evaluated during the course of the infusion study, and also prior to discharge of the study participant. Direct pressure will be applied after the biopsy to prevent bruising and bleeding. Study participants will be given specific instructions prior to discharge to check for signs of hematoma and contact the research team if there is evidence of hematoma. Patients will be instructed to abstain for a minimum of 7 days prior to the infusion study from anticoagulants, such as aspirin, and will not be allowed to participate in the study if unable to refrain from their use.

Stable Isotopes: Stable isotopes are tested by the manufacturer (Cambridge Isotope Laboratories, Andover, MA) for sterility and pyrogenicity. They are mixed with normal saline prior to infusion. Stable isotope infusates will be prepared by the Pharmacy at Mayo Clinic in Arizona and delivered to the CSIU the morning of the study. Stable isotope tracers are naturally occurring compounds and are not radioactive. Stable isotopes are already present in the body in varying amounts. The stable isotopes will increase the level of naturally occurring isotopes by <7%. By making small elevations in the concentration of these stable isotopes in the blood, and by monitoring their changes over time in blood, as well as measuring their incorporation in muscle proteins, we will be able to determine the metabolism of muscle proteins. Any adverse reactions during the isotope infusion that suggest allergic reaction or infection will be promptly addressed by the physician. Depending on the seriousness of the reaction, the infusion study will be terminated. Thus, the risk of this procedure is no different than the general risk of infused substances.

Amino Acids Solution: Amino acids will be infused to increase the plasma amino acid concentrations. Per the manufacturer, local reactions consisting of a warm sensation, erythema, phlebitis and thrombosis at the infusion site can occur with peripheral intravenous infusion of amino acids. In such cases the infusion site will be changed promptly to another vein. Generalized flushing, fever and nausea also have been reported during peripheral infusions of amino acid solutions, as well as symptoms of hyperammonemia in the case of excessive rates of infusion or in patients with hepatic insufficiency where may result in plasma amino acid imbalances, hyperammonemia, prerenal azotemia, stupor or coma. Infusion of amino acids is routinely used in research in experiments similar in nature to this research and in clinical practice for the nutritional support of infants and young pediatric patients requiring TPN. Any adverse reaction during the amino acids solution infusion that suggests allergic reaction or infection will be promptly addressed by the physician in charge, and depending on the seriousness of the reaction, the infusion study will be terminated. Per the manufacturer, hypersensitivity to one or more amino acids, severe liver disease or hepatic coma, anuria or metabolic disorders involving impaired nitrogen utilization are contraindications. For that reason, subjects with such conditions will be excluded.

Dual-Energy X-ray Absorptiometry (DEXA): This is a common clinical procedure used to estimate body composition and exposes subjects to a very low amount of radiation. This radiation dose is far less than the amount used during normal chest X-ray. The amount of radiation in a DEXA scan is considered safe for adults, but it may cause damage to unborn babies. For that reason, a urine pregnancy test will be performed just prior to a DEXA scan.

Subject Monitoring: A nurse and/or a physician from the research team will monitor subjects during the infusion study, including the exercise session, and will document observations in the subject's chart. There will always be a medical staff by the bedside for the duration of the infusions. Subjects will be monitored during exercise for abnormal blood pressure and/or heart rate responses. In case of an abnormal response, the study physician will determine the seriousness of the response and whether to discontinue the exercise. If that is the case, subject participation in the infusion study will be terminated. A urine pregnancy test will be performed prior

Date: February 23, 2024

Protocol V11

to each infusion study, and the infusion study will not commence if positive. At the conclusion of the infusion study, the peripheral IVs will be removed and pressure applied to the site until bleeding is no longer apparent. Prior to discharge, biopsy sites will be inspected. Subjects will be given contact numbers and told that they should contact our staff if they perceive anything unusual. Problems subsequent to the study will be brought to the attention of the physician. If the physician sees the subject, a procedure note will be entered into the subject's folder.

Subject Confidentiality: All study data will be collected by the research team, reviewed by the PI and Co-Investigators, and stored in secure, locked files and/or databases in order to protect them from inadvertent loss or improper access. All laboratory specimens, evaluation forms, reports, and other records will be identified by coded number only to maintain subject confidentiality. Information gained from this study that can be linked to the subject's identity will not be released to anyone other than the investigators, the subject, and the subject's physician. All the information obtained in connection with these studies will remain confidential as far as possible within state and federal law. The results of these studies will be published in scientific journals without identifying the subjects by name.

Potential Benefits of the Proposed Research to Human Subjects and Others

There will be no direct benefit to the subjects participating in these studies. Subjects will have access to their screening results, which may alert them to potential health problems. However, the knowledge gained from these studies will have a benefit to society in terms of enhancing our understanding of the biological mechanisms that sustain unfavorable protein metabolism in muscle of humans with obesity, and ultimately improve the level of health in these individuals. The risks to the subjects are minimal and are outweighed by the benefit of the information that will be acquired from the studies.

Importance of the Knowledge to be Gained

The metabolism of proteins is impaired in skeletal muscle of humans with obesity. These studies are designed to understand the underlying cellular mechanism(s) that contribute to impaired skeletal muscle protein metabolism in these individuals. Unfavorable content and distribution of specific proteins (i.e., myosin heavy chain isoforms) in the muscle of humans with obesity is associated with unhealthy metabolic profile. Acute exercise and increase in plasma amino acids will be used as investigational tools to modulate the metabolism of muscle proteins, and in order to unravel biological mechanisms that sustain the unfavorable protein metabolism in muscle of humans with obesity. Findings from these studies will provide important knowledge that is necessary in order to favorably modify proteins with important metabolic implications in skeletal muscle of humans with obesity.

Bibliography:

2. Wolfe RR. The underappreciated role of muscle in health and disease. *Am J Clin Nutr*. 2006;84(3):475-82. PubMed PMID: 16960159.

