Based on the evidence discussed in above, lower MHC-I gene expression, including MHC-I protein expression, in skeletal muscle results in lower content of Type I fibers in skeletal muscle, and as observed in humans with obesity. We propose to understand biological mechanisms that sustain lower MHC-I expression in muscle of humans with obesity by employing experimental tools that are known to stimulate MHC-I gene expression. In non-obese, healthy humans aerobic exercise increases MHC-I, while decreases MHC-IIx, isoform content in skeletal muscle (52, 61), and there is good evidence showing that exercise can reverse dysregulated metabolism seen in muscle of humans with obesity (50, 62). However, other evidence shows that humans with obesity can be “exercise resistant” (63, 64). Our preliminary evidence shows that, although synthesis of MHC-I fails to increase, mRNA of MHC-I increases immediately after aerobic exercise in subjects with obesity. Therefore, acute exercise can be used as an experimental tool to experimentally manipulate mRNA expression of MHC isoforms, and specifically the slow MHC gene/MYH7 mRNA that is responsible for determining the overall muscle fiber phenotype. Failure to increase the synthesis of MHC-I despite increase in MHC-I mRNA expression after exercise in our preliminary studies provides evidence for “translational resistance” with respect of MHC-I expression. These data, therefore, point to reduced rate of MHC-I translation, as cause, at least in part, for reduced MHC-I synthesis, and thus lower content of MHC-I-containing fibers in muscle of humans with obesity. Increasing the plasma amino acid supply to skeletal muscle stimulates acutely the process of overall translation in muscle (65-68), and by enhancing assembly of the active eIF4F complex (69, 70). We have previously shown that increasing the plasma amino acid concentration alone, increases overall protein synthesis in muscle of humans with obesity (8). We propose to couple the response of increased MHC-I mRNA expression after exercise in subjects with obesity to increased plasma amino acids, and which we will employ as a second experimental tool to experimentally upregulate the overall translation process in skeletal muscle. That way we will discover on whether impaired global translation in muscle contributes to the lower synthesis and thus MHC-I expression in muscle of humans with obesity. We expect increased synthesis rate of MHC-I in the presence of increased plasma amino acids after exercise, suggesting that it is impaired global translation in muscle that

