
Date: February 23, 2024

Protocol V11

contributes to lower synthesis and expression of MHC-I. On the other hand, failure to increase synthesis rate of MHC-I under these conditions, will suggest a defect that is specific to the MHC-I translation. Our studies will, therefore, pinpoint specific biological defects that sustain unfavorable muscle fiber phenotype in humans with obesity, and which is key in any effort to address metabolic abnormalities (i.e., impaired muscle glucose uptake) originating from an unfavorable muscle fiber phenotype in these humans.

Specific Aims

Aim 1. To determine the turnover rate of MHC isoforms and overall muscle protein in skeletal muscle of subjects with obesity and lean controls in the basal state. We hypothesize lower synthesis rate of MHC-I (due at least in part to lower MHC-I mRNA) along with lower overall muscle protein synthesis in skeletal muscle of humans with obesity, and concomitant with lower formation of the eukaryotic initiation factor 4F (eIF4F) in muscle (key protein-complex signaling overall translation/synthesis). We hypothesize that muscle MHC-IIx synthesis is not reduced in obesity, and despite lower eIF4F complex formation in muscle, because the presence of higher MHC-IIx mRNA expression in muscle of humans with obesity.

Aim 2. To determine stimulation of the turnover rate of MHC isoforms in skeletal muscle of subjects with obesity and lean controls by plasma amino acids and with and without prior exercise. We hypothesize that increasing the plasma amino acid concentrations alone increases the basal rate of synthesis across all MHC isoforms in both lean and obese subjects, revealing a response largely dependent upon their respective mRNA expressions. This is because plasma amino acids enhance the overall protein translation in muscle (i.e., increase muscle eIF4F complex formation). We hypothesize that acute aerobic exercise alone does not increase the basal-state MHC-I synthesis rate in either lean or obese subjects, and despite greater increase in MHC-I mRNA expression in muscle of subjects with obesity. Thus, we also hypothesize that coupling the plasma amino acid stimulus to the exercise stimulus will increase the synthesis rate of the MHC-I in the subjects with obesity, revealing that impaired overall muscle protein translation is also responsible (and in addition to lower basal-state MHC-I mRNA, Aim#1) for lower MHC-I expression in muscle of humans with obesity.

Approach

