To test our hypotheses, we propose to study both subjects with obesity and lean controls. Each subject will take part in a single infusion trial. The infusion trial will consist of a Basal study period and an Experimental study period (**Fig. 1**). The Experimental study period will include either an acute session of aerobic exercise following by amino acid infusion (EX+AA trial) or amino acid infusion alone (AA trial). The exercise stimulus is designed to primarily target the MHC-I mRNA expression and synthesis of MHC-I in muscle ((our preliminary evidence for MHC-I mRNA and (63, 64, 82)). The amino acid infusion is designed to specifically upregulate the overall protein translation in muscle (65, 66), and we have shown to increase global (i.e., mixed muscle) protein synthesis in both lean humans as well as humans with obesity (8). Our preliminary evidence does not show increase in the synthesis rates of either mixed-muscle, mitochondrial (data not shown), or MHC-I protein following exercise alone. However, we propose to expand this preliminary evidence in lean humans and humans with obesity. Therefore, we will test the effects of exercise alone (EX trial) in groups of subjects that are separate from the lean and obese subject groups indicated above, and by following same experimental procedures as in the EX+AA trial but without the infusion of amino acids. We will study subjects with obesity (N=9) and lean controls (N=9) to test the hypothesis that exercise alone does not stimulate the synthesis of MHC-I, and despite increase in MHC-I mRNA expression by exercise. With the exception of the exercise session, subjects will be resting in bed for the duration of each trial.

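### A rise in MHC-I synthesis within the obese group does not separate relieved impairment of translation from the normal response to amino acids, and the no-rise reading does not require that the stimuli worked

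*Combined protocol and SAP*

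**What the plan says.** The end of the Significance section sets out two readings of the EX+AA result. The positive one is "We expect increased synthesis rate of MHC-I in the presence of increased plasma amino acids after exercise, suggesting that it is impaired global translation" that contributes to low MHC-I. The negative one is that "failure to increase synthesis rate of MHC-I under these conditions, will suggest a defect that is specific to the MHC-I translation". Aim 2, under Specific Aims, repeats the positive reading for the obese group in firmer terms: coupling the two stimuli "will increase the synthesis rate of the MHC-I in the subjects with obesity, revealing that impaired overall muscle protein translation is also responsible".

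The same Aim 2 hypothesises that "increasing the plasma amino acid concentrations alone increases the basal rate of synthesis across all MHC isoforms in both lean and obese subjects", and gives a general mechanism: "This is because plasma amino acids enhance the overall protein translation in muscle (i.e., increase muscle eIF4F complex formation"). It also hypothesises that exercise alone does not raise MHC-I synthesis in either group. The Experiments section reports that the chosen infusion has been shown to "increase global (i.e., mixed muscle) protein synthesis in both lean humans as well as humans with obesity".

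Statistical Design and Power names a 2-way repeated measures ANOVA without stating its factors or a decisive contrast. Its one power statement for the MHC-I response concerns the increase from Basal in obese EX+AA subjects (17 subjects, 1.15 SD, power above 90%). Lean EX+AA and lean amino-acid-alone (AA) arms of 17 each are enrolled, but neither reading refers to them.

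**The concern.** Amino acids are the step meant to probe translation, and the protocol expects them to work in lean muscle, its reference group. Seeing them work in obese muscle shows that the muscle responds. It does not show that translation was impaired beforehand, or that such an impairment explains low MHC-I.

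The negative reading has a matching gap. A flat MHC-I result points to an MHC-I-specific defect only if MHC-I mRNA rose and general translation was stimulated in the same subjects. The reading does not ask for either, although MHC-I mRNA, eIF4F formation and mixed-muscle synthesis are all listed as main end-points and measured after the manipulation.

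What is at stake is the study's central mechanistic statement. Equal lean and obese responses could be reported as impaired global translation, and a stimulus that failed could be reported as an MHC-I-specific defect.

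**Working it through.** **Step 1: set the protocol's own predictions for MHC-I synthesis side by side.**

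| Condition | Lean | Obese | Source |
|---|---|---|---|
| Exercise alone (EX) | no rise | no rise | Aim 2 |
| Amino acids alone (AA) | rise | rise | Aim 2 |
| EX+AA | not stated | rise | Aim 2 |

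The direction of response is the same in both groups wherever both are predicted. The obese EX+AA rise is also expected from amino acids without exercise, so a rise from Basal does not isolate the coupling of the two stimuli.

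**Step 2: reproduce the planned power.** Inputs from Statistical Design and Power: n = 17, standardised rise d = 2.3/2 = 1.15 SD, paired t-test, alpha 0.05 (0.0125 after Bonferroni). Sidedness is not stated; two-sided is assumed.

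- Noncentrality = d × √n = 1.15 × √17 = 4.74, with 16 degrees of freedom.
- Alpha 0.05: critical t = 2.12, power = 99.3%.
- Alpha 0.0125: critical t = 2.81, power = 96.1%.

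Both agree with the stated figure of above 90%. As a two-sample test with 17 per group, 1.15 SD gives 90.2%, which also agrees. The stated power is sound for the test it describes.

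**Step 3: let the groups respond identically.** Suppose lean and obese EX+AA subjects both rise by 1.15 SD.

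- P(significant rise in obese) = 99.3%.
- P(significant rise in lean) = 99.3%.
- P(significant obese v lean difference in change) = 5%, the test's alpha.

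The finding that triggers the positive reading is thus almost certain with no group difference at all.

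**Step 4: what an obese v lean contrast can detect.** Take the change from Basal in each subject and compare 17 obese with 17 lean: two-sample t, 32 degrees of freedom, two-sided 0.05, critical t = 2.04, noncentrality = d × √(17/2) = 2.915 × d. The documents give no size for this difference, so a range is assumed, in SDs of the change.

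| Difference in change (SD) | Power |
|---|---|
| 0.25 | 11% |
| 0.50 | 29% |
| 0.575 (half of 1.15) | 37% |
| 0.75 | 56% |
| 1.00 | 81% |
| 1.15 | 90% |

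The smallest difference with 80% power is 0.99 SD (noncentrality 2.915 × 0.992 = 2.89), or 1.21 SD at alpha 0.0125. A difference of 0.575 SD would need about 49 per group for 80% power.

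**The case against.** The strongest reply is that Aim 2 is a rescue step built on Aim 1. Aim 1 compares Basal eIF4F formation, mixed-muscle synthesis and MHC-I synthesis between lean and obese subjects. Aim 2 then asks whether synthesis follows once exercise has raised mRNA and amino acids have lifted translation. A normal lean response would not refute a rescue.

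Part of this stands. The overall argument does not rest on the obese group alone, and Aim 1 can show that an impairment exists. It does not make the Aim 2 rise evidence that the impairment causes low MHC-I. The rescue logic also meets the protocol's own predictions: exercise alone is expected to leave MHC-I synthesis unchanged in lean subjects too, and amino acids alone are expected to raise it in obese subjects.

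Some stronger readings are tempting but not supported:

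- **That the protocol claims proof.** Significance speaks only of what a result would suggest; Aim 2 is firmer, but still short of proof.
- **That exercise is hypothesised to raise MHC-I mRNA in obese subjects only.** The phrase "which we show to increase only in the subjects with obesity" describes preliminary data. Aim 2 expects a greater increase in obesity, not an exclusive one.
- **That the AA arms give a clean lean v obese test.** Aim 2 says the amino acid response depends largely on mRNA, and Aim 1 expects lower Basal MHC-I mRNA in obesity. That contrast is confounded too, and a relieved impairment acting on less mRNA could produce an equal or smaller rise.
- **That only a greater-than-lean rise could indicate impairment.** For the same reason, this should not be the sole gate.

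It is also fair that the negative reading presupposes raised mRNA and stimulated translation, and that the infusion was chosen on prior evidence that it works in both groups. What is missing is the explicit check, not the measurement.

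**Conclusion.** The concern holds as an inferential gap, not an arithmetic error. On the protocol's own hypotheses, a rise from Basal within the obese group cannot tell relieved impairment from a normal response, and the no-rise reading lacks a condition that the stimuli took effect.

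The 99% (96% at alpha 0.0125) is the power of the planned within-obese test. It is conditional on a 1.15 SD rise, an equal lean response and two-sided testing. A reader might take it as the rate at which the study would wrongly attribute low MHC-I to translation. The documents do not support that, because Aim 1 supplies a separate lean v obese premise and the true lean response is unknown.

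Two further limits apply. The lean prediction is explicit only for amino acids alone; for EX+AA the protocol is silent on lean subjects. And the ANOVA, with lean arms enrolled, could supply the missing contrast, but it is not named as the basis for either reading.

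**What to change.** Amend the end of Significance, Aim 2, and Statistical Design and Power as follows.

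1. **Positive reading.** Name the obese v lean difference in the Basal-to-Experimental change in MHC-I synthesis (group × period) as the contrast that informs impaired global translation. Report it separately for the AA and EX+AA arms, with Basal MHC-I mRNA and its change alongside. Read it together with Aim 1's Basal eIF4F comparison and with EX+AA against AA and against EX. Report a rise within the obese group alone as responsiveness to amino acids, not as evidence of impairment.
2. **Negative reading.** Conclude an MHC-I-specific defect only if MHC-I mRNA, and eIF4F or mixed-muscle synthesis, rose in the same obese EX+AA subjects while MHC-I synthesis did not. Otherwise report the mechanism as unresolved.
3. **Precision.** State that 17 v 17 detects about 0.99 SD of change with 80% power, and that a 0.575 SD difference has only about 37%.

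This uses subjects, biopsies and assays already planned. The cost is that firm mechanistic conclusions become less likely, and an unresolved result is a real possibility at this sample size.
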